Multiple Imputation (Missing Not At Random) Description

The event rate during off-treatment period (after the treatment discontinuation and before the study close-out) is calculated. The survival time during off-treatment period is assumed to follow exponential distribution of calculated event rate. The survival time during off-treatment

period is added to the survival time during on-treatment period for those subjects who require imputation (ie, early terminators). If the total duration is longer than the period from randomization to study close-out, the survival time will be imputed to the study close-out as a censored observation. Otherwise, the survival time will be imputed to the date of event. Multiple imputation is used to impute the survival time by 5000 iterations.

Procedures:

Step	Description
1	From the ADSL dataset restricted to ITT population (ITTFL='Y'), extract patient identifiers (USUBJID), randomization date (RANDDT), randomized treatment (TRT01PN), death date (DTHDT), treatment (TRT01PN) start (TRTSDT) and stop (TRTEDT) date for treatment, study termination date (WTHDRDT), date of last contact (LASTDT), follow-up after treatment discontinued (FUFL), and stratification factors. Sort dataset by USUBJID.
2	From the efficacy analysis dataset (ADTTE), select the primary endpoint event. Select patient identifiers (USUBJID), randomized treatment (TRT01PN), the censoring indicator (CNSR), follow-up length (ADY), and last contact date (ADT). Sort dataset by USUBJID.
3	Identify patients that discontinued study drug (IPDISC='YES') from the ADDS dataset. Retain USUBJID, analysis start date (ASTDT), and IPDISC variables. Sort dataset by USUBJID.

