4	
Merge ADSL, ADTTE, and ADDS data together to create a dataset for analysis named EFF1.
 
 • Create a variable for start of close out period (e.g., 12 Feb 2022). • Assess if last contact date (ADT) is non-missing and less than end of study date 
 ○ If ADT non-missing and less than study end and patient was censored in the primary analysis then create a variable called COMPLETER and assign a value of 0 (study termination). ○ If ADT non-missing and greater than study end date, or the ADT is greater than the closeout date, or if non-censored in primary analysis then create a variable called COMPLETER and assign a value of 1 (primary endpoint event/completed study). • Assess if patient discontinued study medication (IPDISC='YES'), or was randomized and not treated, and evaluate this based on the censoring status in primary analysis and the COMPLETER status described above. • If IPDISC='YES' and patient was censored in primary analysis (CNSR=1) and did not complete the study (COMPLETER=0) then create a variable indicating the follow-up data will be imputed for the patient (IMPUTE=1). 
 - Create a variable called EVENT and set to missing to hold the censoring indicator used in analysis following multiple imputation. - Create a variable called T2EVENT and set to missing to hold the follow-up time used in analysis following multiple imputation. - Create a variable called T0 to hold the follow-up time from primary analysis (T0=ADY)

Step	Description
	
- Create a variable called T1 to hold the follow-up time from primary analysis (if DTHDT>. then T1=DTHDT – ADT + 1, otherwise T1= 12 Aug 2022 – ADT + 1).
 
 • If patient had a primary endpoint event in the primary analysis (CNSR=0), or completed the trial (CNSR=1 and COMPLETER=1), or patient did not discontinue drug prior to start of close out period (IPDISC ^= ‘YES’) and COMPLETER=1) then create a variable indicating the follow-up data will be not imputed for the patient (IMPUTE=0). 
- Create a variable called EVENT and set equal to 1 (EVENT=1) if patient experienced a primary endpoint event in primary analysis (CNSR=0), and 0 otherwise (EVENT=0).
 
- Create a variable called T2EVENT and set to equal to the follow-up time from primary analysis (T2EVENT=AVAL).
 
Sort dataset by treatment (TRT01PN) and randomization strata

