5	
For patients with IPDISC='Y', and remained in follow-up after discontinuation (ADT>TRTEDT and (DTHDT=. or DTHDT> ADT)), or for patients randomized and not treated that remained in follow-up IPDISC='Y' and (ADT>. and TRTSDT=. and (DTHDT=. or DTHDT> ADT)), sum the number of primary endpoint events (EVENT) by treatment group and randomization strata. Output dataset named EFF_COUNT.

6	
For those same patients from Step 5 sum the person-years of follow-up from discontinuation (TRTEDT) or from RANDDT (when TRTSDT=.) to the earliest of a primary endpoint event, last visit, death, or start of close out period (ADT). Output dataset named EFF_EXP.

7	
Create a dataset called EFF_RATE merging EFF with EFF_COUNT and EFF_EXP by treatment group and primary analysis strata. Derive hazard rates for primary endpoint event for each patient in a new variable named RATE. Set RATE=365.25*(primary endpoint event sum/follow-up time sum).

8	
Create a new dataset called IMPUTE from EFF_RATE restricted to patients that required follow-up imputation (IMPUTE=1). Derive 5,000 follow-up times for each patient for imputation in a variable named T2 as T2 is the randomly sampled from the exponential distribution given the event rate. When generating the exponential random variate specify a SEED equal to 1234 prior to derivation of T2. Assign the sequence of the T2 generated to a variable named ITERATION.

9	
Create a dataset called IMPUTE2 from the IMPUTE dataset. For each of the 5,000 observations created in Step 8, derive variables EVENT=1 and T2EVENT=T0+T2 if T2 is less than the time from study termination (LASTDT) to the earlier of the start of close out period or (post-termination) death (T2< DTHDT - LASTDT if DTHDT>, or T2<Aug 12, 2022 – LASTDT). Otherwise, set T2=0 and T2EVENT equal to the time from randomization to the earlier of the start of close out period, or post-termination) death (whichever occurs first). Here T2EVENT= DTHDT - RANDDT+1 if DTHDT> LASTDT, otherwise T2EVENT=Aug 12, 2022 – RANDDT+1

10	
Create 5,000 (virtual) datasets called IMPUTE3 by concatenating IMPUTE2 (for each iteration) with EFF with restriction to subjects that did not terminate the study (separately). For each of the 5,000 datasets perform a primary analysis (fit a stratified Cox model or KM method). Save parameter estimates for each iteration, and save the iteration variable.

Step	Description

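### The imputation algorithm for sensitivity analysis 3 gives its close-out date two values 181 days apart, and leaves one group of censored subjects with no assigned outcome.

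*SAP*

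**What the plan says.** The overview of the multiple imputation in SAP Appendix A describes a single end of follow-up: if the imputed time runs too long, "the survival time will be imputed to the study close-out as a censored observation".

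The procedure table then uses these dates:

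- **Step 4, close-out variable:** "Create a variable for start of close out period (e.g., 12 Feb 2022".
- **Step 4, `COMPLETER=0`:** "If ADT non-missing and less than study end and patient was censored in the primary analysis". No date is given for study end.
- **Step 4, `COMPLETER=1`:** last contact after the study end date, "or the ADT is greater than the closeout date, or if non-censored in primary analysis".
- **Step 4, `T1`:** "otherwise T1= 12 Aug 2022 – ADT + 1" when there is no death date.
- **Step 6:** off-treatment person-time stops, by its wording, no later than the start of the close-out period.
- **Step 9, in words:** imputation runs "to the earlier of the start of close out period or (post-termination) death".
- **Step 9, in code:** the event test is "T2<Aug 12, 2022 – LASTDT" when there is no death date, and the time without an imputed event is "T2EVENT= DTHDT - RANDDT+1 if DTHDT> LASTDT, otherwise T2EVENT=Aug 12, 2022" minus the randomization date plus 1.

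Section 8.1.2 lists this as sensitivity analysis 3, on the same population as the primary analysis. Section 8.2 repeats all sensitivity analyses except the win ratio for the EMA primary endpoint.

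**The concern.** Steps 4 and 9 use one term for two dates. Step 4 uses it to decide whose observed time is kept, and Step 9 to decide how far everyone else's follow-up is extended. If both dates are programmed as written, a censored subject last seen just after 12 February 2022 can be kept at the observed time, while one who stopped study drug and was last seen just before it is imputed for up to six more months. Subjects on the two sides of the split would be followed to different calendar limits.

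The split also depends on a second, undated milestone and does not cover every combination of its own flags. The trial was stopped early in part because of high discontinuation rates (Section 14.1), and this analysis is meant to address that problem. Who is imputed, who is kept and who disappears should not be left to the programmer's reading.

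**Working it through.** **1. The gap.** Step 4's example date is 12 February 2022 and Step 9's coded date is 12 August 2022. The difference is 181 days, or 181/365.25 = 0.496 years.

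**2. What it does to one subject.** Assume randomization on 12 February 2016, last contact on 12 February 2020, and no recorded death.

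| Limit used | Event imputed if T2 is below | Censoring time otherwise |
|---|---|---|
| 12 Feb 2022 | 731 days | 2193 days |
| 12 Aug 2022 | 912 days | 2374 days |
| Difference | 181 days | 181 days |

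This is the per-subject maximum. An earlier imputed event or a recorded death shortens it.

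**3. Extra chance of an imputed event.** Under the exponential model of the appendix, a subject still event-free on 12 February 2022 has probability 1 − exp(−h × 181/365.25) of an imputed event in the added window. Section 3.2 gives a design placebo hazard of −ln(0.6)/8 = 0.0639 per year and, at a hazard ratio of 0.60, 0.0383 per year for OCA. Those figures belong to the older, narrower composite. The off-treatment rate that the algorithm would use is not in the SAP, so 0.15 per year is an assumption for the expanded composite. For a subject who left three years before 12 February 2022, the probability is multiplied by exp(−3h), the chance of having no imputed event up to that date.

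| h per year | Event-free on 12 Feb 2022 | Left three years earlier |
|---|---|---|
| 0.0383 (design, OCA) | 1.9% | 1.7% |
| 0.0639 (design, placebo) | 3.1% | 2.6% |
| 0.15 (assumed) | 7.2% | 4.6% |

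**4. Overlap in the completer rule.** `COMPLETER=0` turns on study end alone. `COMPLETER=1` is met by passing either study end or close-out. If study end is later than close-out, a censored subject last seen between the two meets both conditions, and the value depends on which statement runs last.

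**5. Coverage of the imputation flag.** Taking Step 4's conditions in turn:

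| Primary analysis | `COMPLETER` | `IPDISC` | Result |
|---|---|---|---|
| Event | 1 | any | `IMPUTE=0` |
| Censored | 1 | any | `IMPUTE=0` |
| Censored | 0 | YES | `IMPUTE=1` |
| Censored | 0 | not YES | neither |

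The last clause of the `IMPUTE=0` rule covers subjects who did not stop study drug, but it also requires `COMPLETER=1`, so it adds nobody. The fourth row receives no `EVENT` and no `T2EVENT`. Step 10 joins the imputed subjects only to those who did not terminate the study, and Step 4 labels `COMPLETER=0` as study termination. The fourth row is therefore dropped. Its size is not given.

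**The case against.** The February date is introduced as an example, so only August is hard-coded. A close-out period has a start and an end, and August could be the undated study end. The slip would then be the label in Step 9 and not the limit. This stands as a caution: the SAP does not show which date is right. It does not remove the contradiction, because Step 9 uses Step 4's own term.

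A reader might infer that imputed subjects are at risk 181 days longer than completers. The SAP does not support that. Completers keep their observed time, Section 8.1.1 censors at last contact, and that contact may itself fall after February.

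A reader might also infer 2 to 7 extra events per 100 imputed subjects and a biased hazard ratio. The upper figure assumes that all 100 are event-free on 12 February 2022 and that the rate is 0.15 per year. The 100 is itself an assumption. More importantly, the longer window adds risk time along with events, at rates specific to arm and stratum, so unequal numbers of early terminators do not by themselves move a Cox estimate. An illustrative simulation assumed 167 subjects per arm, about 120 imputed, two-fold unequal dropout in two of three scenarios, and completers stopped in February as a worst case. It moved the mean log hazard ratio by about 0.01, against a standard error of 0.16 to 0.19.

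`T1` is not used after Step 4, so its August date changes no result. The unassigned group may be small, since it needs a censored subject whose contact ended early without recorded drug discontinuation. The gap in the logic remains.

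**Conclusion.** The inconsistency is real and should be corrected. One named date has two values 181 days apart. Imputed follow-up can pass the date that helps define completion by up to that amount, and the imbalance against completers lies between 0 and 181 days. The completer conditions overlap if study end is later than close-out. One group of ITT subjects is dropped from an analysis stated to use the primary population.

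No bias in the hazard ratio is demonstrated, and any effect of the date mismatch is probably small. That judgement rests on the exponential model in the appendix and on assumed rates and numbers imputed. The effect of dropping the unassigned group cannot be sized from the SAP. The problem is confined to sensitivity analysis 3 and its repeat for the EMA primary endpoint. The primary log-rank test, the significance level and the testing hierarchy are untouched.

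**What to change.** Before unblinding:

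- State the study end date and one close-out date explicitly.
- Use the same dated limit for `COMPLETER` in Step 4, the off-treatment person-time in Step 6, and both the imputation limit and the censoring time in Step 9. Make the words of Step 9 match its code.
- Make the `COMPLETER=0` and `COMPLETER=1` conditions mutually exclusive.
- Assign every remaining censored `COMPLETER=0` subject either to `IMPUTE=1` or to `IMPUTE=0` with observed time, so that all ITT subjects enter Step 10.

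The limit has to be written into the appendix. It cannot be borrowed from the primary analysis, because Section 8.1.1 censors at last contact and defines no administrative cut-off.

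The cost is a short SAP clarification and small changes to the imputation program. No new data are needed.

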8.1.2. Sensitivity Analyses

The following sensitivity analyses will be carried out on the primary endpoint, with different population, strategy to handle the intercurrent events, or summary.

No.	Population	Strategies to address intercurrent events	Population-level summary
1	Subset of primary population, who had no major protocol violations.	Same as primary analysis	Same as primary analysis
2	Same as primary analysis	Same as primary analysis	The 2 treatment groups will be compared using the win ratio (Pocock 2012) using the unmatched method within the bilirubin randomization strata. The 95% confidence interval will be calculated using a bootstrapping method and a p-value will be calculated using the stratified Finkelstein-Schoenfeld test (Finkelstein 1999).
3	Same as primary analysis	Data collected after the intercurrent events to be excluded (while on treatment policy)	For subjects who didn't experience an event before the intercurrent event, multiple imputation will be carried out for time to event based on the available data after the intercurrent event. Details is included in the appendix.
4	Same as primary analysis	Exclude data after 90 days after a patient discontinues IP.	Same as primary analysis.
5	Same as primary analysis	Include only data prior to when a patient starts commercial OCALIVA.	Same as primary analysis.
6	Same as primary analysis	Include only data prior to when OCA was commercially available in the subject's country.	Same as primary analysis.
7	Same as primary analysis	Hypothetical strategy, ie, as if the intercurrent events didn't happen.	Hazard ratio and 95% CI will be estimated using a weighted Cox regression model with Sandwich estimator. The derivation of the weights based on Inverse Probability of Censoring Weighting (IPCW) is detailed in the appendix.

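### The multiple-imputation steps for Sensitivity Analysis 3 never produce a per-day rate yet use the drawn time as days, and separately they mishandle deaths

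*SAP*

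**What the plan says.** SAP Section 8.1.2 lists Sensitivity Analysis 3, in which "multiple imputation will be carried out for time to event based on the available data after the intercurrent event". Section 8.2 carries the Section 8.1.2 sensitivity analyses, except the win ratio, over to the endpoint that is primary for the EMA filing.

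The procedure is in Appendix A, Multiple Imputation (Missing Not At Random) Description:

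- **Introductory paragraph.** Off-treatment survival time is exponential at the observed off-treatment event rate and is added to the on-treatment time. If the total runs past study close-out, the subject is censored there.
- **Step 4.** Imputation applies to subjects who discontinued product, were censored in the primary analysis and did not complete the study. For them EVENT is set to missing and T0 is set to ADY. It also says "Create a variable for start of close out period (e.g., 12 Feb 2022").
- **Step 5.** Off-treatment events are counted in subjects who "remained in follow-up after discontinuation (ADT>TRTEDT and (DTHDT=. or DTHDT> ADT")).
- **Step 6.** For the same subjects, "sum the person-years of follow-up from discontinuation (TRTEDT") or from randomization if never treated. ADT is the earliest of event, last visit, death or close-out.
- **Step 7.** "Set RATE=365.25*(primary endpoint event sum/follow-up time sum").
- **Step 8.** "T2 is the randomly sampled from the exponential distribution given the event rate".
- **Step 9.** "derive variables EVENT=1 and T2EVENT=T0+T2 if T2 is less than the time from study termination (LASTDT") to the earlier of close-out and death. Otherwise T2 is set to 0, and "Here T2EVENT= DTHDT - RANDDT+1 if DTHDT> LASTDT", with 12 August 2022 as the limit if there was no such death.

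Appendix A, Standard Calculations, defines time to event in days.

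**The concern.** T2 is compared with differences between calendar dates and added to a follow-up time in days. The exponential rate therefore has to be per day, and multiplying by 365.25 moves it away from a daily rate. A rate that is too high makes T2 too short, so imputed subjects are given events soon after last contact when most should be censored at close-out.

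The handling of death is a second, separate problem. All-cause death is a Group 1 component of the primary endpoint. Even so, the Step 5 filter removes subjects whose first event is death, and Step 9 assigns no status to a death known to have followed study termination.

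Section 14.1 says the trial was stopped early due in part to high discontinuation rates. A reader will look to this analysis to learn how far dropout could have shaped the result. If a programmer repairs the steps silently, the repair is not prespecified.

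**Working it through.** **1. What unit the rate must have.** Step 9 sets T2 against 12 August 2022 minus LASTDT, or DTHDT minus LASTDT, both in days. It also forms T0 + T2 with T0 in days. Write r for the yearly off-treatment rate, events/person-years. The rate needed is r/365.25 per day.

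**2. What Step 7 gives.**

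- Reading A, denominator in person-years (Step 6): RATE = 365.25 x r. This is too large by 365.25 x 365.25, about 133,400.
- Reading B, denominator in days: RATE = 365.25 x events/(365.25 x person-years) = r, a yearly rate. T2 is then in years but used as days, and RATE is too large by 365.25.

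**3. Size.** The imputation steps state no numerical result to reproduce, and the off-treatment rate is not given, so r is assumed. With residual follow-up t in years:

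- unit-consistent: P(event) = 1 - exp(-r x t)
- Reading A: P = 1 - exp(-365.25 x r x 365.25 x t)
- Reading B: P = 1 - exp(-r x 365.25 x t)

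| r per year | t | Unit-consistent | Reading A | Reading B |
|---|---|---|---|---|
| 0.10 | 2 years | 1 - exp(-0.2) = 18% | about 100% | 1 - exp(-73.05), about 100% |
| 0.05 | 1 year | 1 - exp(-0.05) = 5% | about 100% | 1 - exp(-18.3), about 100% |
| 0.20 | 3 years | 1 - exp(-0.6) = 45% | about 100% | about 100% |
| 0.01 | 1 year | 1.0% | about 100% | 97% |
| 0.01 | 3 months | 0.2% | about 100% | 60% |

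At r = 0.10 the mean T2 should be 365.25/0.10 = 3,652.5 days. It is 1/36.525 = 0.03 day under Reading A and 1/0.10 = 10 days under Reading B.

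**4. Cross-check with the design hazards (Section 3.2).** Placebo: -ln(0.6)/8 = 0.0639 per year. OCA: 0.60 x 0.0639 = 0.0383 per year. As a check on these inputs, Freedman's formula at a hazard ratio of 0.60 gives 126 events (127 stated). Four years of accrual in a 10-year study gives 384 subjects, and 384/0.90 = 427 (428 stated). With these hazards the unit-consistent probability is 6.2% / 3.8% (placebo / OCA) at 1 year and 17.4% / 10.9% at 3 years. Reading B gives 99.7% / 97.0% at only 3 months; Reading A gives 100%.

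Passing RATE as a scale parameter does not help. Mean T2 is then 23 / 14 days under Reading A and under 1 day under Reading B.

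**5. Deaths in Step 5.** If the first primary event is death, ADT equals DTHDT. The strict inequality fails, so the subject leaves both the event count and, through Step 6, the person-time. Every excluded subject has an event, so the exclusion ordinarily lowers the rate.

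**6. Event status in Step 9.** EVENT enters as missing from Step 4. One branch sets it to 1; the other sets T2 and T2EVENT only. The introductory paragraph supplies censoring at close-out, although Step 9 does not code it. Nothing supplies a status for a known post-termination death that precedes the drawn event time. The unit error largely hides this gap, because almost no draw reaches that branch until the units are corrected.

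**7. Close-out date.** 12 February to 12 August 2022 is 181 days. With correct units at r = 0.10, moving from 2 years to 2 years plus 181 days changes 18% to 1 - exp(-0.2496) = 22%.

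**The case against.** The best defence is that the intention is clear. Multiplying events per day by 365.25 is the ordinary way to express a rate per person-year, so Step 7 probably means a yearly rate, and the fault is one omitted conversion when T2 is used. This makes Reading B the likelier one and the 0.03-day figure the extreme case. That stands, but Reading B still gives about 100%, and the missing conversion appears nowhere in Steps 7 to 9.

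Several stronger inferences are not supported:

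- A reader might infer that the death faults add to the near-100% result. They do not. They remove events, and the near-100% figure comes from the units alone.
- A reader might infer that censoring at close-out is unspecified. The introductory paragraph specifies it; only the coding in Step 9 is missing.
- A reader might infer that the plan fixes two contradictory close-out dates. Step 4 gives 12 February 2022 only as an example, so this is a point to clarify.
- A reader might infer that the hazard ratio would reflect only who left early in each arm. Under Step 4, completers and subjects with an observed primary event keep their observed time and status. The number to be imputed is not in the SAP, so the effect on the hazard ratio cannot be sized.
- A reader might infer that nothing else addresses informative dropout. Sensitivity Analysis 7 (IPCW) models censoring with baseline and time-varying covariates.

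**Conclusion.** The unit error holds on the text under either reading of the denominator. Coded as written, T2 is too short by 365.25 or 365.25 squared, and nearly every imputed subject with more than a few months to close-out receives an event soon after last contact. The probability is about 100% against 18% at an assumed 0.10 per year and 2 years. Over 0.05 to 0.20 per year and 1 to 3 years the correct range is 5% to 45%. Only at a very low assumed rate with short residual follow-up does Reading B fall clearly below this, for example 60% at 0.01 per year and 3 months.

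The exclusion of first-event deaths in Step 5 and the unassigned post-termination death in Step 9 are separate faults that work in the opposite direction. They do not offset the unit error, and they would remain after it is repaired.

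The scope is Sensitivity Analysis 3, for the primary endpoint and for the EMA primary endpoint. The primary log-rank test and the IPCW analysis are unaffected. The sizes are per-subject probabilities under assumed rates, not shifts in the hazard ratio.

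**What to change.** In Appendix A, before the analysis is run:

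1. **Step 7:** set RATE = events/(365.25 x person-years), so that T2 is in days, and state the unit in Steps 6 to 9. In Step 8, state that RATE is a rate and not a scale parameter.
2. **Step 5:** use DTHDT >= ADT, so that a death that is the first primary event counts, with its person-time.
3. **Step 9:** set EVENT = 0 when close-out comes first. For a known post-termination death reached before the drawn event time, set EVENT = 1 at the death date, subject to the rule in Section 8.1.1 that only adjudicated events are analysed. The plan should say whether such deaths are adjudicated.
4. **Steps 4 and 9:** name one close-out date and use it throughout.

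The cost is a few lines of SAP text and code. No new data are needed, and the primary analysis does not change.

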3.2. Sample Size Determination

The following assumptions were used in the Protocol Version 6 sample size calculations:

- Exponential survival curves, placebo survival estimate of 0.6 at 8 years with a hazard ratio of 0.60, and total study duration of 10 years (from first subject enrolled), allowing for 4 years of subject accrual and 6 years of follow up.
- Subjects will be randomized in a 1:1 ratio to placebo or OCA.
- The 2 treatment groups will be compared using a 2-sided log rank test at the 5% level of significance.
- Two interim analyses and one final analysis are planned, with interim analyses occurring after the accrual of 50% and 75% of clinical outcome events, respectively.
- A dropout rate of 10% is assumed

Based on the randomization ratio, significance level, and assumed hazard ratio, a total of 127 events (both groups combined) was to provide 80% power to demonstrate a statistically significant difference between OCA and placebo on time to liver-related outcomes, including all-cause mortality.

In addition, based on the remaining assumptions stated above, it was estimated that approximately 428 subjects would be enrolled to attain 127 events.

Sample size calculations were based on the following composite endpoint: time to first occurrence of death, liver transplant, MELD ≥ 15 , uncontrolled ascites, or hospitalization for new onset or recurrence of variceal bleed, hepatic encephalopathy, or spontaneous bacterial peritonitis.

Due to enrollment challenges and difficulties to keep patients in the study, the trial will be terminated early by sponsor. To better evaluate the benefit-risk ratio, the composite endpoint will be revised to include additional components that occur earlier in the progression of PBC

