Percentages based on frequency counts will be based on available data, and denominators will generally exclude missing values, unless otherwise stated. For frequency counts of categorical variables, categories whose counts are zero will be displayed for the sake of completeness. For example, if none of the subjects discontinued due to “lost to follow-up,” this reason will be included in the table with a count of 0. Percentages based on frequency counts will be presented as a whole number (no decimal places), and values less than 1% will be presented as “<1%.” Values less than 100% but that round up from 99.5% to 100% will be presented as “>99%.”

Quantitative laboratory tests containing less than (<) and greater than (>) symbols are test results that are below and above quantifiable limits, respectively. In order to retain these values for analysis purpose, the following imputations will be done within the analysis datasets:

For laboratory test results that are below the quantifiable limit:

Imputed laboratory results = (numeric portion of the result) x 0.9.

For laboratory test results that are above the quantifiable limit:

Imputed laboratory results = (numeric portion of the result) x 1.1.

For the purpose of tabulations, the unscheduled post-baseline values generally will be excluded from summary tables, but will be included in data listings. Unscheduled visits will be considered for analyses of shift from baseline to worst value (low-normal-high).

Standard Calculations

Variables requiring calculation will be derived using the following formulas:

- First dose date is defined as the day of first dose of IP received after randomization
- Last dose date is defined as day of the last dose of IP
- Time to event – The time to an event will be calculated in days as the date of the first occurrence of the event minus the date of first investigational product administration plus 1
- Days – A duration expressed in days between one date (*date1*) and another later date (*date2*) will be calculated using the following formulas:

duration in days = $date2 - date1 + 1$, where $date1 \geq$ first dose date

duration in days = $date2 - date1$, where $date1 <$ first dose date

- Months – A duration expressed in months is calculated as the number of days divided by 365.25/12 (approximately 30.4)
- Years – A duration expressed in years between one date (*date1*) and another date (*date2*) is calculated using the following formulas:

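### The multiple-imputation steps draw event times from a rate in the wrong unit, so nearly every imputed early terminator fails almost at once

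*SAP*

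**What the plan says.** The procedure is in SAP Appendix A, Multiple Imputation (Missing Not At Random) Description. It serves sensitivity analysis 3 in Section 8.1.2. Section 8.2 extends all the sensitivity analyses except the win ratio to the endpoint that is primary for the EMA filing.

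The steps that matter are:

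- **Step 4:** "Create a variable called T0 to hold the follow-up time from primary analysis (T0=ADY"). Under Standard Calculations in the same appendix, "The time to an event will be calculated in days as the date of the first occurrence of the event", so T0 is in days.
- **Step 6:** "sum the person-years of follow-up from discontinuation (TRTEDT"), by treatment group and randomization stratum.
- **Step 7:** "Set RATE=365.25*(primary endpoint event sum/follow-up time sum").
- **Step 8:** "T2 is the randomly sampled from the exponential distribution given the event rate". No unit is given for T2.
- **Step 9:** "derive variables EVENT=1 and T2EVENT=T0+T2 if T2 is less than the time from study termination (LASTDT") to the close-out date or a later death. The comparison is written as a difference of dates: "T2< DTHDT - LASTDT if DTHDT>".

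**The concern.** Step 9 works entirely in days: T0, the date differences and the censoring times are all day counts. T2 must therefore be in days, which requires an exponential rate per day. The factor 365.25 in Step 7 does the opposite. It turns a daily rate into a yearly one, or inflates a rate that is already yearly. T2 then comes out in years, or in a still longer unit, and is used as days without conversion.

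The imputed times would collapse towards zero and almost every imputed subject would be given an event shortly after leaving. The analysis is meant to test robustness to missing follow-up, and Section 14.1 says the trial stopped early partly because of high discontinuation rates, so the imputed group may be large. An artefact there could make a real effect look absent or reversed, or could produce an apparent effect from unequal drop-out.

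**Working it through.** **1. Units.** Take a made-up cell with 10 events in 150 person-years (150 × 365.25 = 54,787.5 person-days).

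- Needed by Step 9: 10 / 54,787.5 = 0.000183 per day.
- Step 7 with follow-up in days: 365.25 × 10 / 54,787.5 = 0.0667. This is the yearly rate, 365.25 times too large for use with days.
- Step 7 with follow-up in person-years, as Step 6 says: 365.25 × 10 / 150 = 24.35. This is 365.25² ≈ 133,400 times too large.

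The mean of T2 is 1/RATE, so it is too short by the same factors.

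**2. Size at the plan's design hazards.** The SAP gives no off-treatment rate. As an illustration, Section 3.2 assumes "Exponential survival curves, placebo survival estimate of 0.6 at 8 years with a hazard ratio of 0.60". That gives:

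- placebo: −ln(0.6)/8 = 0.0639 per year
- OCA: 0.60 × 0.0639 = 0.0383 per year

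These apply to the narrower Version 6 endpoint, so a range of rates follows in item 3. The chance of an imputed event is 1 − exp(−rate × remaining time), with both in the same unit.

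| Placebo / OCA | Consistent units | As written, follow-up in days | As written, person-years |
|---|---|---|---|
| Mean T2, used as days | 5,720 / 9,534 | 15.7 / 26.1 | 0.04 / 0.07 |
| P(event), 3 months left | 1.6% / 1.0% | 99.7% / 97.0% | about 100% |
| P(event), 1 year left | 6.2% / 3.8% | over 99.99% | about 100% |
| P(event), 2 years left | 12.0% / 7.4% | about 100% | about 100% |
| P(event), 4 years left | 22.5% / 14.2% | about 100% | about 100% |

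For placebo with two years left, the consistent figure is 1 − exp(−0.0639 × 2) = 0.120. As written with follow-up in days, it is 1 − exp(−0.0639 × 730.5) = 1 − exp(−46.6), which is 1 for practical purposes.

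**3. Range of rates, follow-up in days (the milder reading).**

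| Yearly rate | Event within 8 weeks | Event within 1 year | Within 1 year, consistent units |
|---|---|---|---|
| 0.01 | 43% | 97.4% | 1.0% |
| 0.02 | 67% | 99.9% | 2.0% |
| 0.05 | 94% | over 99.99% | 4.9% |
| 0.10 | 99.6% | over 99.99% | 9.5% |
| 0.20 | about 100% | over 99.99% | 18.1% |

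**4. Effect on the hazard ratio.** This is a simulation on assumed inputs, to show direction only. It used 334 subjects (the approximate enrolment in Section 5 of the Clinical Pharmacology Analysis Plan), uniform entry over 6 years, close-out at 7 years, the design hazards above (true hazard ratio 0.60), exponential drop-out, imputation from the true rate, and 150 trials per scenario. Cells show hazard ratio (mean number of events).

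| Yearly drop-out, placebo / OCA | Consistent units | As written, days | As written, person-years |
|---|---|---|---|
| 0.10 / 0.10 | 0.60 (61) | 0.84 (145) | 0.85 (146) |
| 0.15 / 0.10 | 0.59 (61) | 0.63 (158) | 0.64 (159) |
| 0.10 / 0.15 | 0.60 (60) | 1.14 (159) | 1.15 (160) |

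In consistent units the hazard ratio stays near 0.60 whatever the drop-out pattern. As written, it moves from 0.63 to 1.15 with the drop-out pattern alone.

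**The case against.** The strongest reply is that this is one of seven sensitivity analyses. The primary test is the stratified log-rank test in Section 8.1.1, and neither the alpha level nor the testing order in Section 8.6 depends on analysis 3. Analyses 4 to 7 in Section 8.1.2 address discontinuation or commercial OCA in other ways. This stands: the error cannot change the primary p-value.

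A second reply is that the paragraph above the steps describes the method sensibly, and that a programmer could convert T2 to days in Step 8, where no unit is stated. An event rate near 100% among imputed subjects would also stand out in the output. This is possible, but the steps are written at program level, with variable names, a seed and date formulas, and contain no conversion. A silent correction would be an undocumented departure from the plan.

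A third reply is that the size depends on rates the SAP does not give. That is true of the details. Failure within weeks fits the days reading at about 0.05 per year or more. At 0.01 to 0.02 it is weeks to months, and on the person-years reading it is the day of leaving. A treatment-by-stratum cell with no off-treatment events has a rate of zero and would impute none. The drop-out rates and calendar in the simulation are assumptions. None of this removes the unit error.

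**Conclusion.** The error is in the text and holds on either reading of the follow-up sum. T2 is too short by a factor of 365.25 or about 133,400. Followed as written, and in every cell with at least one off-treatment event, the steps give an event within a year to 97% or more of imputed subjects with at least a year left, for any yearly rate of 0.01 or higher. In consistent units the figure is 1% at 0.01 per year and 6.2% at the design placebo rate.

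That conclusion rests only on the units in Steps 4 to 9 and the exponential formula. The simulated hazard ratios rest on assumed drop-out, entry and close-out, and do not predict this trial's result. As specified, sensitivity analysis 3 is uninterpretable for both the primary endpoint and the EMA primary endpoint, and should be corrected before it is run.

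**What to change.** Use one unit throughout:

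- **Step 6:** sum follow-up in person-days.
- **Step 7:** RATE = events / person-days, without the factor 365.25.
- **Step 8:** state that T2 is in days, drawn from an exponential with mean 1/RATE, and say what is done when a cell has no off-treatment events.
- **Step 9:** no change of unit is then needed.

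Equivalently, compute a true yearly rate (events / person-years) and use 365.25 × T2 in Step 9.

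A useful program check is to compare the mean imputed event fraction over the 5,000 iterations with the average over imputed subjects of 1 − exp(−RATE × days remaining). Days remaining run to the earlier of close-out and post-termination death. The two should agree closely, not exactly.

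While editing, reconcile the close-out dates: Step 4 gives 12 Feb 2022 as an example, whereas the formulas in Steps 4 and 9 use 12 Aug 2022. This does not affect the finding.

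The unit correction costs a line or two of the appendix and the program, with no new data.
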